## Protocol Synopsis

### I. Protocol Title:

A Phase I/IIa Open-Label, Dose-Escalation Study to Determine the Safety, Tolerability, and Efficacy of AR100DP1 in Healthy Subjects, and Subjects with Mild to Moderate Atopic Dermatitis

### II. Objectives:

#### Primary objective(s):

Phase I: To determine the maximum tolerated dose (MTD) of AR100DP1 in healthy subjects

Phase IIa: To assess the efficacy of AR100DP1 in treating atopic dermatitis (AD)

#### Secondary objective(s):

Phase I: To evaluate the safety and tolerability of AR100DP1 in healthy subjects

Phase IIa: To evaluate the safety, tolerability and efficacy of AR100DP1 in subjects with mild to moderate atopic dermatitis

### III. Test Product:

1. **Name:** AR100DP1 (containing 1.25%, 2.5%, or 5% of drug substance, AR100-DS1)

2. **Dosage form:** Ointment

3. **Strength:** 20 g/tube

0.25 g AR100-DS1/20 g (1.25%)

0.50 g AR100-DS1/20g (2.5%)

1.00 g AR100-DS1/20g (5%)

4. **Dosage and administration:**

#### Dosage:

1.25%, 2.5% and 5% AR100DP1

**IV. Developmental phase:**  First-in-human trial

Phase  I  II  III  IV  Others

**V. Study design:**

1.  Control:  placebo  active  other  
 Uncontrolled
2. Blinding:  open-label  evaluator blind  single blind  double blind  
 double dummy  other
3. Randomized:  yes  no
4.  Parallel  Cross-over  Others (Phase I: 3+3 Dose escalation)
5. Duration of treatment: 14 days for Phase I, 28 days for Phase IIa
6. Titration:  forced  optional  none
7.  Multi-national  Multi-center (Taiwan)  Single center

**VI. Endpoints:**

**1. Primary endpoint(s):**

**Phase I:** Determine the MTD of AR100DP1

*MTD is defined as the highest dose level at which < 2 of 6 subjects experienced a dose limiting toxicity (DLT) during Visit 2-6 (DLT observation period).*

**Phase IIa:** Proportion of subjects with the Investigator's Global Assessment (IGA) score of 0 or 1 on Day 29.

**2. Secondary endpoint(s):****Phase I:**Safety:

- Incidence of adverse events (AE) and serious adverse events (SAE) during Visit 2-6
- Change from baseline in vital signs at Visit 2-6
- Abnormality in physical examination at Visit 2-6
- Transition from baseline in electrocardiogram (ECG) result at Visit 3-6
- Change from baseline in laboratory parameters at Visit 3-6

**Phase IIa:**Efficacy:

- Proportion of subjects achieving the Investigator's Global Assessment (IGA) score of 0 (clear) or 1 (almost clear) on Day 8, Day 15, Day 22, Day 36 and Day 43
- Change from baseline of target lesion area(s) on Day 8, Day 15, Day 22, Day 29, Day 36, and Day 43
- Change from baseline in pruritus NRS of itch level on target lesion area(s) on Day 8, Day 15, Day 22, Day 29, Day 36 and Day 43
- Change from baseline in signs of atopic dermatitis (erythema, edema/papulation, excoriation and lichenification) with grading from 0 (none) to 3 (severe) on target lesion area(s) on Day 8, Day 15, Day 22, Day 29, Day 36 and Day 43
- Change from baseline in the total score of the Patient-Oriented Eczema Measure (POEM) on Day 8, Day 15, Day 22, Day 29, Day 36 and Day 43

Safety:

- Incidence of AE and SAE during Visit 2-8
- Change from baseline in vital signs at Visit 2-8
- Abnormality in physical examination at Visit 2-8
- Transition from baseline in ECG result at Visit 3-8
- Change from baseline in laboratory parameters at Visit 3-8

Exploratory:

- Fold change of IgE on Day 15 and Day 29 compared to baseline on Day 1 ( $IgE_{D15}/IgE_{D1}$ ,  $IgE_{D29}/IgE_{D1}$ )
- Fold change of IL-4 on Day 15 and Day 29 compared to baseline on Day 1 ( $IL-4_{D15}/IL-4_{D1}$ ,  $IL-4_{D29}/IL-4_{D1}$ )

**VII. Selection criteria:****1. Main inclusion criteria****Phase I:**

- (1) Dated and signed informed consent
- (2) Either gender,  $\geq 20$  years old (the legal age of consent majority is 20 years old in Taiwan)
- (3) Healthy subjects, who have no clinically relevant abnormalities, identified by medical history, physical examination, 12-lead electrocardiogram (ECG), and clinical laboratory tests
- (4) Subjects who are willing and able to comply with all scheduled visits, treatment plan, laboratory tests, and other study procedures
- (5) Healthy skin on which reddening can be easily recognized in the area of the test fields, evaluated by the investigator
- (6) Subject of childbearing potential must agree to use abstinence to intercourse, or highly effective contraceptives from signing informed consent to 14 days after the last dose of study drug administration.

At least two forms of effective birth control must be adopted for contraception, and one of which must be a barrier method. Acceptable forms include:

- Established use of oral, injected or implanted hormonal methods of contraception
- Placement of an intrauterine device (IUD) or intrauterine system (IUS)
- Barrier methods of contraception: condom (highly recommended with spermicide), or occlusive cap (diaphragm or cervical/vault caps)

### Phase IIa:

- (1) Dated and signed informed consent
- (2) Either gender,  $\geq 20$  years old (the legal age of consent majority is 20 years old in Taiwan)
- (3) Confirmed clinical diagnosis of atopic dermatitis (based on the criteria of Hanifin and Rajka for AD)
- (4) With at least 0.5% body surface area (BSA) as target lesion area(s)
- (5) Clinical diagnosis of AD that has been clinically stable, which means the IGA score stays as 2 or 3 when evaluated for  $\geq 4$  weeks at the investigator's discretion prior to Screening Visit
- (6) With Investigator's Global Assessment (IGA) score of 2 (mild) or 3 (moderate) at screening
- (7) Subject of childbearing potential must agree to use abstinence to intercourse, or highly effective contraceptives from signing informed consent to 14 days after the last dose of study drug administration.

At least two forms of effective birth control must be adopted for contraception, and one of which must be a barrier method. Acceptable forms include:

- Established use of oral, injected or implanted hormonal methods of contraception
- Placement of an intrauterine device (IUD) or intrauterine system (IUS)
- Barrier methods of contraception: condom (highly recommended with spermicide),

or occlusive cap (diaphragm or cervical/vault caps)

## 2. Main exclusion criteria

### Phase I:

- (1) Subjects who have any visible skin disease at the application site which, in the opinion of the investigator, will interfere with the evaluation of the test site reaction
- (2) Subjects who have a history of AD, psoriasis and/or active AD/eczema
- (3) Subjects who have damaged skin in or around the test sites, including sunburn, excessively deep tans, uneven skin tones, tattoos, scars, excessive hair, numerous freckles, or other disfigurements of the test site
- (4) Evidence or history of clinically significant hematological, renal, endocrine, pulmonary, gastrointestinal, cardiovascular, hepatic, psychiatric, neurological, or allergic disease (including drug allergies, but excluding untreated, asymptomatic, seasonal allergies at the time of dosing)

### Phase IIa:

- (1) Unstable or actively infected AD judged by the investigator
- (2) Active or potentially recurrent dermatologic condition other than atopic dermatitis that may confound evaluation (e.g. fungal infection), judged by the investigator
- (3) Received systemic medication including corticosteroid, immunosuppressant, anti-histamine, phototherapy, or other therapy, which could affect AD within 4 weeks before Screening. However, subjects are allowed to enter the study if subjects have been taking at least 2 weeks of fixed dose anti-histamine prior to Screening and this application does not affect the study judged by the investigator
- (4) Received topical medication including corticosteroid, immunosuppressant, anti-histamine, phototherapy, calcineurin inhibitors, or other therapy for AD on the target lesion area(s) within 1 week before Screening

### The following exclusion criteria are applied for all subjects in Phase I/IIa study:

- (5) Plan to receive immunosuppressive agents (including azathioprine, mycophenolate, cyclophosphamide, chlorambucil, methotrexate, cyclosporine), or systemic steroid with equivalent dosage higher than prednisolone 30 mg/day for more than 14 days at Screening
- (6) Unwilling or unable to comply with the criteria in Life Style Guidelines (Section IX 1.) during the study
- (7) History of use of biologic therapy (including intravenous immunoglobulin) within 12 weeks or 5 half-lives (whichever is longer) prior to Screening
- (8) Received any other investigational drug within 4 weeks prior to Screening

- (9) Required or received systemic CYP3A4 inhibitors with strong potency within 1 week prior to screening, including but not limited to clarithromycin, itraconazole, nefazodone and atazanavir, evaluated by the investigator
- (10) Treatment for any type of cancer (except squamous cell carcinoma, basal cell carcinoma, or carcinoma in situ of the skin, curatively treated with cryosurgery or surgical excision only) within 5 years before screening
- (11) Had surgery within 4 weeks prior to Screening Visit, or plan to have surgery during the study
- (12) Allergies requiring acute or chronic treatment at the investigator's discretion
- (13) Known hypersensitivity to any of the components of the study drug
- (14) Active clinically serious infection or history of human immunodeficiency virus (HIV) infection
- (15) Any of the following serum test abnormalities:
  - Total bilirubin  $> 1.5 \times$  ULN
  - AST or ALT  $> 3.0 \times$  ULN
  - Serum albumin  $< 2.5 \text{ g/dL}$
  - Creatinine  $> 1.5 \times$  ULN
  - Any other  $\geq$  Grade 2 (grading of vaccine clinical trials for Phase I and NCI-CTCAE v5.0 for Phase IIa) laboratory abnormality at baseline (other than those listed above)
- (16) With ongoing acute diseases or within the past 2 years serious medical conditions (e.g. concomitant illness) such as cardiovascular (e.g. New York Heart Association (NYHA) grade III or IV), hepatic (e.g. Child-Pugh Class C), psychiatric condition (e.g. alcoholism, drug abuse), medical history, physical findings, or laboratory abnormality that in the investigators' opinion could interfere with the results of the trial or adversely affect the safety of the subject
- (17) Female subject who is lactating or has positive urine pregnancy test at screening
- (18) Other conditions not suitable for participating in this study judged by the investigator

The DLT is defined as any adverse event (AE)  $\geq$  Grade 2 (Guidance for Industry: Toxicity Grading Scale for Healthy Adult and Adolescent Volunteers Enrolled in Preventive Vaccine Clinical Trials, issued by United States Food and Drug Administration in September 2007), that is considered to be causally related (possibly, probably, or definitely related) to AR100DP1 as judged by the investigator during Visit 2-6 (DLT observation period). The definition of Grade 5 (death related to AE) was added to this grading system as it was not defined in the guidance. The safety results will be reviewed by the Data and Safety Monitoring Board (DSMB) after the completion of each cohort. The DSMB will provide the comments of the decision and determine if it is safe to proceed to the next dose level or stopping the dose escalation. For safety concern, the DSMB will consider to postpone the dose escalation and recruit more subjects into the concurrent dose cohort for evaluation of safety information. The DSMB will give its recommendation of the RP2D while the sponsor will determine the dosage applied in the subsequent Phase IIa study.

In the single-arm Phase IIa study, 12 evaluable subjects with mild to moderate AD are planned to be enrolled and treated with AR100DP1 at the dose determined by the sponsor for 28 days of AR100DP1 treatment period followed by a 14-day follow-up period.

## 1. Participating Duration

**Phase I:** Approximately 6 weeks, including up to 2 weeks of screening, maximal 2 weeks of treatment, and 2 weeks of follow-up.

**Phase IIa:** Approximately 8 weeks, including up to 2 weeks of screening, 4 weeks of treatment and 2 weeks of follow-up.

## 2. Study Schedule

### Phase I

#### ➤ Screening (Visit 1)

*(Day -14 - Day -1)*

- Obtain the signed informed consent form
- Assign subject identifier number
- Obtain demographic characteristics
- Obtain medical history
- Obtain medication history
- Check eligibility
- Perform urine pregnancy test
- Check vital signs
- Obtain weight and height
- Perform physical examinations
- Perform ECG
- Obtain blood samples for laboratory tests
- Record concomitant medications
- Record adverse events

#### ➤ Treatment Period (Visit 2)

*(Day 1)*

- Obtain vital signs (prior to and at least 30 minutes after IP administration at site)
- Perform physical examinations (prior to and at least 30 minutes after IP administration at site)
- Dispense diary and IP
- Record concomitant medications
- Record adverse events

#### Before Dosing:

- Check eligibility
- Perform ECG
- Recording of the test skin area(s) of 750 cm^2 from chest and abdomen

#### Dosing:

- Perform IP administration at site and record in the diary

#### ➤ Treatment Period (Visit 3)

*(Day 8, ± 1 day)*

- Obtain vital signs
- Perform physical examinations

- Perform ECG
- Obtain blood samples for laboratory tests
- Dispense diary and IP
- Retrieve diary and IP
- Record concomitant medications
- Record adverse events

➤ **Treatment Period (Visit 4, End of Treatment (EOT))**

*(Day 15, ± 2 days)*

- Perform urine pregnancy test
- Obtain vital signs
- Perform physical examinations
- Perform ECG
- Obtain blood samples for laboratory tests
- Retrieve diary and IP
- Record concomitant medications
- Record adverse events

➤ **Follow-up Period (Visit 5, Follow-up)**

*(Day 22, ± 3 days)*

- Obtain vital signs
- Perform physical examinations
- Perform ECG
- Obtain blood samples for laboratory tests
- Record concomitant medications
- Record adverse events

➤ **Final Visit (Visit 6)**

*(Day 29, ± 3 days)*

*When the decision of withdrawal is made after the treatment period (Visit 4, EOT) has been completed, subjects should come back for the assessments at Final Visit within 7 days after the decision is made*

- Perform urine pregnancy test
- Obtain vital signs
- Obtain weight
- Perform physical examinations
- Perform ECG
- Obtain blood samples for laboratory tests
- Record concomitant medications
- Record adverse events

➤ **Unscheduled Visit (UV)**

*Unscheduled visit will be arranged when investigator considered necessary or subjects have concerns. Activities to be performed will be at the investigator's discretion and will be documented in the eCRF.*

- Perform urine pregnancy test
- Obtain vital signs
- Perform physical examinations
- Perform ECG
- Obtain blood samples for laboratory tests
- Dispense diary and IP
- Retrieve diary and IP
- Record concomitant medications
- Record adverse events
- Other activities per Investigator's decision

➤ **Early Termination Visit (ET)**

*ET, early termination, is defined as the decision of withdrawal is made prior to Visit 4. Subjects will be requested to complete the coming scheduled visit as ET Visit within 7 days after the last dose.*

- Perform urine pregnancy test
- Obtain vital signs
- Obtain weight
- Perform physical examinations
- Perform ECG
- Obtain blood samples for laboratory tests
- Retrieve diary and IP
- Record concomitant medications
- Record adverse events

**Phase IIa**

➤ **Screening (Visit 1)**

*(Day -14 - Day -1)*

- Obtain the signed informed consent form
- Assign subject identifier number
- Obtain demographic characteristics
- Obtain medical history
- Obtain medication history
- Check eligibility

- Perform urine pregnancy test
- Check vital signs
- Obtain weight and height
- Perform physical examinations
- Perform ECG
- Obtain blood samples for laboratory tests
- Evaluate the IGA score of subjects with AD for eligibility
- Selection, measuring, and recording of target lesion area(s)
- Record concomitant medications
- Record adverse events

➤ **Treatment Period (Visit 2)**

*(Day 1)*

- Obtain vital signs (prior to and at least 30 minutes after IP administration at site)
- Perform physical examinations (prior to and at least 30 minutes after IP administration at site)
- Dispense diary and IP
- Record concomitant medications
- Record adverse events

Before Dosing:

- Check eligibility
- Perform ECG
- Evaluate the IGA score
- Self-evaluation of pruritus NRS on target lesion area(s)
- Evaluate signs of atopic dermatitis on target lesion area(s)
- Self-evaluation of POEM score
- Obtain blood sample for tests of immune response (IgE, IL-4)
- Measuring and recording of target lesion area(s)

Dosing:

- Perform IP administration at site and record in the diary

➤ **Treatment Period (Visit 3)**

*(Day 8, ± 1 day)*

- Obtain vital signs
- Perform physical examinations
- Perform ECG
- Obtain blood samples for laboratory tests
- Evaluate IGA score
- Self-evaluation of pruritus NRS on target lesion area(s)

- Evaluate signs of atopic dermatitis on target lesion area(s)
- Self-evaluation of POEM score
- Measuring and recording of target lesion area(s)
- Dispense diary and IP
- Retrieve diary and IP
- Record concomitant medications
- Record adverse events

➤ **Treatment Period (Visit 4)**

*(Day 15, ± 2 days)*

- Obtain vital signs
- Perform physical examinations
- Perform ECG
- Obtain blood samples for laboratory tests
- Evaluate IGA score
- Self-evaluation of pruritus NRS on target lesion area(s)
- Evaluate signs of atopic dermatitis on target lesion area(s)
- Self-evaluation of POEM score
- Obtain blood sample for tests of immune response (IgE, IL-4)
- Measuring and recording of target lesion area(s)
- Dispense diary and IP
- Retrieve diary and IP
- Record concomitant medications
- Record adverse events

➤ **Treatment Period (Visit 5)**

*(Day 22, ± 2 days)*

- Obtain vital signs
- Perform physical examinations
- Perform ECG
- Obtain blood samples for laboratory tests
- Evaluate IGA score
- Self-evaluation of pruritus NRS on target lesion area(s)
- Evaluate signs of atopic dermatitis on target lesion area(s)
- Self-evaluation of POEM score
- Measuring and recording of target lesion area(s)
- Dispense diary and IP
- Retrieve diary and IP
- Record concomitant medications
- Record adverse events

- **Treatment Period (Visit 6, End of Treatment (EOT))**  
(Day 29, ± 2 days)
  - Perform urine pregnancy test
  - Obtain vital signs
  - Perform physical examinations
  - Perform ECG
  - Obtain blood samples for laboratory tests
  - Evaluate IGA score
  - Self-evaluation of pruritus NRS on target lesion area(s)
  - Evaluate signs of atopic dermatitis on target lesion area(s)
  - Self-evaluation of POEM score
  - Obtain blood sample for tests of immune response (IgE, IL-4)
  - Measuring and recording of target lesion area(s)
  - Retrieve diary and IP
  - Record concomitant medications
  - Record adverse events
- **Follow-up Period (Visit 7, Follow-up)**  
(Day 36, ± 3 days)
  - Obtain vital signs
  - Perform physical examinations
  - Perform ECG
  - Obtain blood samples for laboratory tests
  - Evaluate IGA score
  - Self-evaluation of pruritus NRS on target lesion area(s)
  - Evaluate signs of atopic dermatitis on target lesion area(s)
  - Self-evaluation of POEM score
  - Measuring and recording of target lesion area(s)
  - Record concomitant medications
  - Record adverse events
- **Final Visit (Visit 8)**  
(Day 43, ± 3 days)  
*When the decision of withdrawal is made after the treatment period (Visit 6, EOT) has been completed, subjects should come back for the assessments at Final Visit*
  - Perform urine pregnancy test
  - Obtain vital signs
  - Obtain weight
  - Perform physical examinations

- Perform ECG
- Obtain blood samples for laboratory tests
- Evaluate IGA score
- Self-evaluation of pruritus NRS on target lesion area(s)
- Evaluate signs of atopic dermatitis on target lesion area(s)
- Self-evaluation of POEM score
- Measuring and recording of target lesion area(s)
- Record concomitant medications
- Record adverse events

➤ **Unscheduled Visit (UV)**

*Unscheduled visit will be arranged when investigator considered necessary or subjects have concerns. Activities to be performed will be at the investigator's discretion and will be documented in the eCRF.*

- Perform urine pregnancy test
- Obtain vital signs
- Perform physical examinations
- Perform ECG
- Obtain blood samples for laboratory tests
- Evaluate IGA score
- Self-evaluation of pruritus NRS on target lesion area(s)
- Evaluate signs of atopic dermatitis on target lesion area(s)
- Self-evaluation of POEM score
- Obtain blood sample for tests of immune response (IgE, IL-4)
- Measuring and recording of target lesion area(s)
- Dispense diary and IP
- Retrieve diary and IP
- Record concomitant medications
- Record adverse events
- Other activities per Investigator's decision

➤ **Early Termination Visit (ET)**

*ET, early termination, is defined as the decision of withdrawal is made prior to Visit 6. Subjects will be requested to complete the coming scheduled visit as ET Visit within 7 days after the last dose.*

- Perform urine pregnancy test
- Obtain vital signs
- Obtain weight
- Perform physical examinations

- Perform ECG
- Obtain blood samples for laboratory tests
- Evaluate IGA score
- Self-evaluation of pruritus NRS on target lesion area(s)
- Evaluate signs of atopic dermatitis on target lesion area(s)
- Self-evaluation of POEM score
- Obtain blood sample for tests of immune response (IgE, IL-4)
- Measuring and recording of target lesion area(s)
- Retrieve diary and IP
- Record concomitant medications
- Record adverse events
- Other activities per Investigator's decision

### **3. Study Intervention Discontinuation and Subject Withdrawal for Discontinuation**

#### **3.1 Study Intervention Discontinuation**

When the discontinuation is confirmed, subjects will be requested to complete the coming scheduled visit as early termination (ET) Visit within 7 days after the last dose. When the decision of withdrawal is made at the scheduled visit prior to the end of treatment (EOT), that same visit will be deemed as ET Visit, which means the assessments scheduled for ET will be evaluated. When the decision of withdrawal is made at an Unscheduled Visit, the same Unscheduled Visit will be deemed as ET Visit and the assessments at this visit will follow those defined at ET visit. When the decision of withdrawal is made after the treatment period (EOT) has been completed, subjects are requested to return for assessments scheduled at Final Visit within 7 days after the decision is made. AEs will be followed up until resolved or stable. Alternatively, if the subject does not agree to this option or is not able to physically attend the visit, a modified follow up by telephone contact should be arranged, if agreed to by the subject and in compliance with local data privacy laws/practices.

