## X. Statistics:

1. **Primary hypothesis:**  superiority  non- inferiority  equivalence  other
2. **Sample size:** Enrolled 35 subjects (Phase I: 21 subjects/Phase IIa: 14 subjects)  
Evaluable 30 subjects (Phase I: 18 subjects/Phase IIa: 12 subjects)
3. **Efficacy population:**  ITT  PP (Phase IIa only)  Other (PP-EOT, Phase IIa only)

**Safety population:**  ITT  PP  Other (MTD, Phase I only)

Intent-to-treat (ITT) population:

- Enrolled subjects receiving at least one dose of AR100DP1

MTD population (Phase I Only):

- Eligible subjects who administered at least one dose of the investigational product and experienced DLT
- OR
- Eligible subjects who were dosed for at least 12 days with at least 85% of compliance.

Per-protocol before End of Treatment (PP-EOT) population (Phase IIa Only):

- A subset of ITT population
- Fulfill all inclusion and exclusion criteria
- Subjects dosed for at least 21 days of Phase IIa with at least 75% of compliance
- No major protocol deviation which could affect the efficacy assessment

- Not take any prohibited therapy before End of Treatment (EOT) Visit assessment

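### Phase I: a DLT-free subject can count toward the MTD on 12 days' dosing and 85% compliance without being observed to Visit 6, where the DLT window ends

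*Combined protocol and SAP*

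**What the plan says.** **DLT window.** Section VI.1 and the DLT definition in Section VIII run the Phase I observation period from Visit 2 to Visit 6. Visit 6 is Day 29 ± 3, so Day 26 to 32. Section VIII allows escalation on 0 DLTs in 3 subjects or 1 in 6.

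**Who counts.** Section X, item 3, gives two routes into the MTD population. A subject with a DLT enters after a single dose. A DLT-free subject enters under this rule: "Eligible subjects who were dosed for at least 12 days with at least 85% of compliance". It sets a minimum exposure and no minimum observation.

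**Leaving before the end of treatment (EOT).** Section VIII.3.1 says "subjects will be requested to complete the coming scheduled visit as early termination (ET) Visit within 7 days after the last dose". If the decision is made at a scheduled visit before EOT, "that same visit will be deemed as ET Visit"; an unscheduled visit is treated likewise. For Phase I, Section VIII.2 says "ET, early termination, is defined as the decision of withdrawal is made prior to Visit 4". In Phase IIa the cut-off is Visit 6. Neither schedule table in Section XI places anything after the early-termination (ET) visit.

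**Leaving after EOT.** The Final Visit assessments are done within 7 days of the decision (Section VIII.3.1; Section XI, note m).

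**What remains open.** "AEs will be followed up until resolved or stable". If a subject declines or cannot attend, "a modified follow up by telephone contact should be arranged", with no date set. Section VIII.2 adds: "Unscheduled visit will be arranged when investigator considered necessary or subjects have concerns".

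Phase I completers are seen again at Visits 5 and 6, each with vital signs, examination, ECG and laboratory tests.

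**The concern.** The evaluability rule and the DLT window do not match. A subject can satisfy the first and be scored DLT-free although the second was only partly observed. Two groups are affected:

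- (a) subjects with a last dose on about Day 12 to 14 who decide to withdraw before Visit 4, and whose last scheduled check is the ET visit;
- (b) subjects who complete Visit 4 and withdraw soon after, so that their Final Visit comes before the Visit 6 window opens.

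This is a first-in-human trial with very small cohorts, so one subject is a third or a sixth of the evidence for escalating. A DLT is any related adverse event of Grade 2 or higher on the vaccine-trial toxicity scale. Exclusion criterion (15) applies that scale to laboratory abnormalities, so a DLT could be silent. A visit prompted by the subject's own concerns would not find it.

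**Working it through.** **1. The plan's own thresholds.** Section V gives 14 days of treatment and Section III gives two applications a day: 14 × 2 = 28 applications. 85% of 28 is 23.8, so 24 applications are needed, which is 12 full days. The two parts of the rule agree. The 18 evaluable subjects equal 3 cohorts × 6.

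**2. Which last doses qualify** (uninterrupted dosing, compliance measured against 28):

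| Last dose | Applications | Compliance | In MTD population if DLT-free |
|---|---|---|---|
| Day 11 | 22/28 | 78.6% | no |
| Day 12 | 24/28 | 85.7% | yes |
| Day 13 | 26/28 | 92.9% | yes |
| Day 14 | 28/28 | 100% | yes |

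If compliance were measured against doses due up to stopping, Day 12 would still qualify, and Day 11 would still fail the 12-day part.

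**3. Group (a): unchecked time to Day 29.** The coming scheduled visit is Visit 4, Day 15 ± 2 = Day 13 to 17.
- ET in that window: 29 − 17 = 12 to 29 − 13 = 16 days, or 12/29 = 41% to 16/29 = 55% of the 29 days.
- Only the 7-day limit applied, last dose Day 12: ET on Day 12 to 19, leaving 29 − 19 = 10 to 29 − 12 = 17 days.
- Same, last dose Day 13: ET on Day 13 to 20, leaving 9 to 16 days.
- Same, last dose Day 14: ET on Day 14 to 21, leaving 8 to 15 days.
- Against the earliest permitted Visit 6 (Day 26), ET in the Visit 4 window leaves 26 − 17 = 9 to 26 − 13 = 13 days.

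**4. Group (b).** A decision on Day 16 puts the Final Visit no later than 16 + 7 = Day 23. That is 3 days before the Visit 6 window opens and 6 days before Day 29. Any decision up to Day 18 gives a visit by Day 25, still before Day 26.

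**5. Who is not affected.** A completer with a last dose on Day 14 is seen at Visit 6, 26 − 14 = 12 to 32 − 14 = 18 days later. A subject with 12 dosing days whose EOT visit falls on Day 13 is also a completer (14 to 20 days) and is unaffected unless he or she withdraws later. DLT-free subjects who stop by Day 11 are already outside the MTD population.

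**6. Possible effect on one escalation step.** The documents give no DLT timing, so this is an illustration on assumed values. Let p be the true DLT risk and f the share of DLTs that arise after the last check and go unseen. With one such subject among three, P(no DLT seen) = (1 − p)² × (1 − p(1 − f)); with full observation it is (1 − p)³.

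| p | Full observation | f = 10% | f = 25% | f = 50% |
|---|---|---|---|---|
| 20% | 0.512 | 0.525 | 0.544 | 0.576 |
| 33% | 0.301 | 0.316 | 0.338 | 0.375 |
| 50% | 0.125 | 0.138 | 0.156 | 0.188 |

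For example, 0.67² × (1 − 0.33 × 0.75) = 0.4489 × 0.7525 = 0.338.

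**7. Phase IIa.** With a last dose on Day 21 and ET at Visit 5 (Day 21 to 24), 43 − 24 = 19 to 43 − 21 = 22 days to Day 43 have no scheduled check. If Visit 5 was already held and ET is at Visit 6 (Day 27 to 28), it is 15 to 16 days.

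**The case against.** The strongest reply is that the harm needs a chain of events. A subject must apply almost the full course, withdraw without a DLT within a few days, be clean on Day 8 and at the last visit, and then develop a related Grade 2 event after stopping a topical product. Nothing in the documents suggests late onset. This stands as a limit on how often the problem would arise. It does not explain why the rule should count a subject whose window was not observed.

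The safeguards also deserve credit. The DSMB reviews each cohort and can add subjects, and DLT incidence is shown on both the ITT population and evaluable subjects. The schedule tables label unscheduled visits as available during the study period, which favours their staying open after ET. All this makes it less likely that such a subject is taken at face value, but none of it schedules a laboratory test or ECG.

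A reader might infer that early stoppers are abandoned after the ET visit. The text does not support that: known adverse events are followed until they settle, and a symptomatic new event can lead to an unscheduled visit. What is missing is scheduled detection of new or silent events.

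Finally, Section X, item 4, assesses the MTD on evaluable subjects and never says that these are the MTD population. It is the only matching set, but the link is inferred.

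**Conclusion.** The point holds for Phase I. The rule can score a subject as DLT-free without observation to Visit 6. For group (a) with ET in the Visit 4 window, 12 to 16 days to Day 29 go without a scheduled check. On the 7-day limit alone it is 9 to 17 days for a last dose on Day 12 or 13, and 8 to 15 for Day 14. For group (b) the shortfall is smaller, about 6 days in the example. The plan gives no expected number of such subjects, and it is probably small.

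The conclusion rests on uninterrupted twice-daily dosing and on evaluable subjects meaning the MTD population.

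Two stronger readings are not supported. One is that the MTD will be set too high: the documents contain nothing on late DLTs, and the probabilities above are assumptions. The other is that the Phase IIa result is compromised: its primary endpoint is IGA on Day 29, and no decision rule depends on late safety data. There the gap only makes adverse-event capture through Visit 8 less complete for early leavers.

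**What to change.** **Main change (Section X, item 3).** Extend the second MTD criterion: at least 12 dosing days, at least 85% compliance, *and* DLT status assessed, including laboratory tests, in the Visit 6 window (Day 29 ± 3). A DLT-free subject who misses this is not evaluable and is replaced. State the replacement rule, and state that evaluable subjects means this population. Telephone contact alone should not suffice, because it cannot find a laboratory DLT. This one edit covers both groups.

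Cost: the plan has 21 − 18 = 3 spare Phase I places. Each replacement exposes one more healthy volunteer to a first-in-human product and can delay a cohort by about 6 weeks, including screening. A subject with nearly complete dosing is lost to the MTD count but stays in the ITT presentation of DLTs.

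**Secondary change (Sections VIII.2 and VIII.3.1; Section XI, notes l and m).** Separate stopping the ointment from leaving the study. Ask subjects who stop early and keep their consent to attend the existing Final Visit safety assessments about 14 days after the last dose, with a telephone call about adverse events as the fallback. In Phase I, subjects meeting the exposure rule should attend within the Visit 6 window. For last doses on Day 12, 13 or 14, adding 14 days gives Day 26, 27 or 28, so one visit serves both purposes. Cost: one visit of procedures already defined, which some subjects will decline.
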